4.4 SUBJECTS OF REPRODUCTIVE POTENTIAL

Male subjects who are sexually active with a partner of child-bearing potential must use, with their partner, a condom plus an approved method of highly acceptable contraception from the time of informed consent until 90 days after last dose of study drug.

The following methods are acceptable:

- Combined (estrogen and progestogen containing) hormonal contraception associated with inhibition of ovulation:
 - oral
 - intravaginal
 - transdermal
- Progestogen-only hormonal contraception associated with inhibition of ovulation:
 - oral
 - injectable
 - implantable intrauterine device
 - intrauterine hormone-releasing system
- Surgical sterilization (vasectomy or bilateral tubal occlusion)

Female subjects who are not of child-bearing potential do not need to use any methods of contraception. A woman is considered of childbearing potential, unless they are at least 2 years post-menopausal or permanently sterile. Permanent sterilization methods include hysterectomy, bilateral salpingectomy and bilateral oophorectomy.

Female subjects who are sexually active and are of child-bearing potential must use, with their partner, an approved method of highly effective contraception from the time of informed consent until 90 days after the last dose of study drug.

The following methods are acceptable:

- Combined (estrogen and progestogen containing) hormonal contraception associated with inhibition of ovulation and a barrier method (ie, condom for male partner):
 - oral
 - intravaginal
 - transdermal
- Progestogen-only hormonal contraception associated with inhibition of ovulation and a barrier method (ie, condom for male partner)
 - oral
 - injectable
 - implantable intrauterine device
 - intrauterine hormone-releasing system
- Surgical sterilization (vasectomy or bilateral tubal occlusion)

Alternatively, true abstinence is acceptable when it is in line with the subject's preferred and usual lifestyle. If a subject is usually not sexually active but becomes active, they, with their partner, they must comply with the contraceptive requirements detailed above.

4.4.1 Sperm and Egg Donation

Male subjects should not donate sperm and female subjects should refrain from egg donation for the duration of the study and for at least 90 days after the last day of study medication administration.

4.4.2 Pregnancy

Subjects will be instructed that if they/their partner become pregnant during the study this should be reported to the investigator. The investigator should also be notified of pregnancy occurring during the study but confirmed after completion of the study. In the event that a subject/subject's partner is subsequently found to be pregnant after the subject is included in the study, then consent will be sought from the partner and, if granted, any pregnancy will be followed and the status of mother and/or child will be reported to the Sponsor after delivery.

Any subject reporting a pregnancy during the study will be withdrawn from the study and should complete the taper schedule.

4.5 REMOVAL OF SUBJECTS FROM THERAPY OR ASSESSMENT

While subjects are encouraged to complete all study evaluations, subjects may voluntarily withdraw from the study for any reason at any time. They may be considered withdrawn if they fail to return for visits, or become lost to follow-up for any other reason.

If premature withdrawal occurs for any reason, the investigator must make a genuine effort to determine the primary reason for a subject's premature withdrawal from the study and record this information on the electronic case report form (eCRF). All subjects who withdraw from the study with an ongoing AE must be followed until the event is resolved or deemed stable. If a subject withdraws prematurely after dosing, all data to be collected prior to discharge from the clinical site should be collected at the time of premature discontinuation or at the scheduled discharge.

For subjects who are lost to follow-up (ie, those subjects whose status is unclear because they failed to appear for study visits without stating an intention to withdraw), the investigator should show "due diligence" by documenting in the source documents the steps taken to contact the subject (eg, dates of telephone calls, registered letters).

Subjects must be discontinued from the study for the following reasons, if deemed appropriate by the Sponsor or investigator:

1. Development of signs or symptoms indicative of cardiac valvulopathy or regurgitation (mitral, aortic, tricuspid, pulmonary valves), or pulmonary hypertension for which IDSMC, in consultation with the IPCAB, the central cardiac reader, and the investigator believe the benefit of continued participation does not outweigh the risk.
2. Subject is found to have entered the clinical investigation in violation of the protocol.
3. Subject requires or starts using the use of an unacceptable or contraindicated concomitant medication.
4. Subject's condition changes after entering the clinical investigation so that the subject no longer meets the inclusion criteria or develops any of the exclusion criteria.
5. Subject is noncompliant with procedures set forth in the protocol in an ongoing or repeated manner.
6. Subject experiences an AE that warrants withdrawal from the clinical investigation.

7. Clinically significant worsening of seizures, judged by investigator or subject/caregiver such that treatment outside of the protocol and other than ZX008 is assumed to be in the subject's best interest. Frequent or increased use of rescue medication may be considered indicative of worsening.
8. An "actual suicide attempt" as classified by the Columbia-Suicide Severity Rating Scale (C-SSRS).
9. It is the investigator's opinion that it is not in the subject's best interest to continue in the study.
10. Subject is found to be pregnant while on study.

Discontinuation decisions will be made at each participating site by the site investigator, except that discontinuations due to development of cardiovascular or cardiopulmonary complications are to be made by the IDSMC with input from the IPCAB and the investigator.

If feasible, the process of discontinuation should be discussed with the Medical Monitor. The decisions regarding the discontinuation of the investigational therapy, whether the study medication should be stopped immediately or tapered should be discussed with the Medical Monitor, but final decisions about the process will remain at the discretion of the site principal investigator.

Subjects who are discontinued from the clinical investigation (Cohort 2) for any reason will not be replaced.

Subjects may withdraw their consent to participate in the study at any time without having to justify the reason for doing so. The decision to withdraw consent and discontinue participation in the study will not prejudice the subject's future medical treatment in any way. Subjects must be discontinued from receiving ZX008 and/or participating in any further study procedures under the following circumstances:

- The subject or the subject's legally authorized representative wishes to discontinue participation in the study.
- The investigator advises that the subject's safety or well-being could be compromised by further participation in the study.
- The Sponsor requests that a subject discontinues participation in the study (eg, due to suspicion of fraud, multiple enrollments in clinical studies, lack of compliance, etc).

The IDSMC may request that the study be terminated after review of the safety information at any time during the study. The IDSMC will review the data for the development of heart valve disease and pulmonary hypertension as they occur on a case-by-case basis and at regular meetings.

In the event that the study is terminated prematurely then the procedure for termination should be followed as described in [Section 3.6](#). Concern for the interests of the subject will always prevail over the interests of the study.

The reason for, and date of discontinuation from participation in the study must be recorded in detail in the eCRF and in the subject's medical records (eg, AEs, lack of compliance, lost to follow-up, etc). If possible, the subject/subject's legal representative should confirm his decision in writing.

The investigator will attempt to complete all procedures usually required at the end of the study at the time when the subject's participation in the study is discontinued or as close as possible to that time. Specific procedures required are described in [Section 6.1.5](#), [Section 6.2.5.10](#), and [Section 6.2.5.11](#). As far as possible, a complete final examination must be performed on all subjects who do not complete the study according to the study protocol.

Data collected until the time a subject discontinues participation in the study will be handled in the same manner as data for subjects completing the study. Where possible, further information will be collected if any AEs are experienced by a subject after discontinuing participation in the study.

4.6 TERMINATION OF THE CLINICAL STUDY

If the investigator, the Sponsor, the Medical Monitor, or the IDSMC becomes aware of conditions or events that suggest a possible hazard to subjects if the clinical study continues, then the clinical study may be terminated. The clinical study may be terminated at the Sponsor's discretion at any time also in the absence of such a finding.

Conditions that may warrant termination of the clinical study include, but are not limited to:

- The discovery of an unexpected, relevant, or unacceptable risk to the subjects enrolled in the clinical study.
- Failure to enroll subjects at the required rate.
- A decision of the Sponsor to suspend or discontinue development of ZX008.

4.7 REPLACEMENT OF SUBJECTS

Approximately 25 subjects will be screened for Cohort 1 to ensure that subjects enter the study and complete all PK assessments; participants who discontinue prior to completion of all study-related procedures may be replaced. Approximately 115 subjects will be screened for Cohort 2 to randomize approximately 90 subjects into the T + M Period; randomized subjects will not be replaced.

4.8 ELIGIBILITY FOR EXTENSION TRIAL

Subjects from Cohort 1 who complete the PK portion of this study or subjects from Cohort 2 who complete the 12-week Maintenance Period of this study will be eligible to enrol in a planned, separate, open-label extension trial of ZX008 if they meet Inclusion/Exclusion criteria for that study are deemed eligible for continued participation in a trial of fenfluramine. Cohort 1 subjects must have tolerated the IMP and the Investigator also must feel that the subject would benefit from long term therapy with ZX008 for other multiple seizure types, eg, pattern sensitivity, photosensitivity, severe absences, nocturnal seizures, severe myoclonus which are not managed with current therapy. Subjects from Cohort 1 may not enter the separate, open-label extension trial until the dose for Cohort 2 has been selected.

Those subjects who do not complete the PK phase or the 12-week Maintenance Period of the study may, on a case-by-case basis, be eligible for entrance into the separate open-label extension trial after consideration of the circumstances of the early termination and the potential benefit-risk of continued participation in a ZX008 trial. The decision whether to permit open-label extension trial participation resides solely with the Sponsor, who may consult with the site investigator, the IPCAB and/or the IDSMC.

5. INVESTIGATIONAL MEDICINAL PRODUCT INFORMATION

ZX008/matching placebo will be administered in the current study. A brief description of the ZX008 product is provided below ([Table 4](#)).

Table 4. Investigational Medicinal Product – ZX008

	Study Product
Substance Code	ZX008
Active Substance (INN)	Fenfluramine hydrochloride
Trade Name	Not applicable
Formulation (including dosage form and strength)	Solution 1.25, 2.5, and 5 mg/mL
Route/Mode of Administration	Oral
Manufacturer	PCI Pharma Services on behalf of Zogenix International Limited

The IMP(s) will be administered by the oral route.

Background medications (Cohort 1): On the day prior to dosing (Day -1) the parents/caregivers will be reminded to bring the subject's usual epilepsy medications (CLB + VPA or CLB + VPA + STP) and any other epilepsy medications the patient may be taking, to the CRU on the day of dosing (Day 1) for AM and PM administration, as applicable.

5.1 IDENTITY OF INVESTIGATIONAL MEDICINAL PRODUCT

ZX008 drug product is an oral aqueous solution of fenfluramine hydrochloride buffered to pH 5 and provided in concentrations of 1.25 mg/mL, 2.5 mg/mL, and 5 mg/mL. The excipients selected have been approved for use in the formulations of currently marketed drug products and are considered to be safe. The solution formulations will be suitably flavored and colored, and will contain preservatives and a thickening agent. The product is sugar free and is intended to be compatible with a KD.

The formulation will be provided in bottles with tamper-evident, child-resistant caps. The clinical trials material will be supplied in 1 bottle size with nominal fill volume of 120 mL. Matching placebo for Cohort 2 also will be provided. Doses to be studied include 0.2 mg/kg and 0.4 mg/kg for Cohort 1 during the PK portion of the study; subjects will receive ZX008 at a fixed dose of 0.2 mg/kg/day in the Cohort 1 transition period. Dosing for Cohort 2 was informed based on evaluation of Cohort 1 and Study ZX008-1505 data, and assigned to be 0.5 mg/kg/day and no more than 20 mg/day.

If the parent/caregiver for Cohort 2 is unable to administer the full dose due to spillage (eg, dose was spilled during measuring, subject spit dose out during administration), he/she should attempt to give the full dose noting the extra amount used to fulfill the dose. **Care must be taken not to overdose.** If the amount spilled is not known, the parent/caregiver should not give additional medication to avoid potential overdose.

5.1.1 Packaging and Labeling

The ZX008 product will be packaged and labeled according to current International Conference on Harmonization (ICH), Good Manufacturing Practices (GMP), and Good Clinical Practices (GCP) guidelines, and national legal requirements.

Dosing directions for the product can be found in the IMP handling instructions for the study subjects and for the investigator.

5.2 DESCRIPTION OF REFERENCE TREATMENT, COMPARATOR, AND/OR PLACEBO

Placebo solution is identical in aspect and composition to ZX008 and is composed of identical ingredients used in the ZX008 formulation, except that it does not contain the active ingredient, fenfluramine hydrochloride.

No comparators or reference treatments will be used.

5.2.1 Packaging and Labeling

Placebo solution will be packaged in an identical manner to ZX008. The matching placebo product will be packaged and labeled according to current ICH, GMP, and GCP guidelines, and national legal requirements.

Dosing directions for the product can be found in the IMP handling instructions for the study subjects and for the investigator.

5.3 SHIPMENT AND STORAGE

IMP will be supplied to the study sites by the Sponsor or its delegate.

All IMP will be transported, received, stored, and handled strictly in accordance with the container or product label, the instructions supplied to the research site and its designated pharmacy, the site's standard operating procedures, and applicable regulations. IMP must be stored separately from normal hospital or practice inventories, in a locked facility with access limited to the investigator and authorized personnel. The investigator must ensure that the IMP is dispensed only to subjects enrolled in this study according to this study protocol.

Appropriate storage temperature and transportation conditions will be maintained for the study drug from the point of manufacture up to delivery of the study drug. Study medication must be stored at 15-25°C with excursions of 5-30°C permitted; do not freeze.

Storage and handling instructions of the IMP maintained at the subject's home are described in the subject's IMP handling instructions.

All unused IMP will be saved by the site for final disposition according to the Sponsor's directive.

5.4 IMP ACCOUNTABILITY

The investigator or delegate will confirm receipt of all shipments of the IMP in writing using the receipt form(s) provided by the Sponsor or vendor.

For both cohorts, assignment of IMP to the subject will be handled through an interactive voice randomization (IVR) or Interactive Web Response (IWR) platform. The investigator or delegate will be required to register the subject through IVR/IWR and all study medication will be assigned to the subject through the IVR/IWR. The IVR/IWR will also maintain a log of all received and dispensed medication.

All supplies must be accounted for throughout the study using the study drug accountability form. At the end of the study, the dated and signed (by the investigator or delegate, eg, pharmacist) original drug accountability form must be retained at the study site as verification of final drug accountability.

Records for the delivery of the IMP to the study site, the inventory at the study site, the use by each subject (use by subject will be documented in the subject diary), and the destruction or return of the IMP to the Sponsor must be maintained by the investigator (or delegate). The records will include dates, quantities, batch numbers, and unique code numbers assigned to the IMP and to the subjects. The investigator must maintain records documenting that subjects were provided with the doses of the IMP specified in this study protocol. Furthermore, the investigator must reconcile all IMPs received from the Sponsor. The investigator must provide reasons for any discrepancies in drug accountability. Forms will be provided by the Sponsor to ensure standardized and complete drug accountability.

5.5 TREATMENT ADMINISTRATION

5.5.1 Cohort 1: Randomization

For Cohort 1, participants in Regimen 1 and Regimen 2 will be randomized to open-label treatment, stratified by age. A randomization schedule will be produced for these two regimens and provided to the sites. Subjects who enter the study on CLB + VPA will be randomized to treatment with a single dose of ZX008 0.2 mg/kg added to their usual dose of CLB + VPA (Regimen 1) or a single dose of ZX008 0.4 mg/kg added to their usual dose of CLB + VPA (Regimen 2). Randomization will be stratified by age ensure that both Regimens 1 and 2 have at least 2 subjects < 6 years old and at least 2 subjects \geq 6 years old. Subjects who enter the study on STP + CLB + VPA will be assigned to Regimen 3 (ZX008 0.2 mg/kg + CLB + VPA + STP).

5.5.2 Cohort 2: Randomization

For subjects who enter Cohort 2, upon completion of the Baseline Period, subjects who qualify for the study will be randomized (1:1) in a double-blind manner to receive either treatment with ZX008 (0.5 mg/kg/day, 20 mg/day maximum) or placebo. The randomization will be stratified by age (< 6 years, \geq 6 years) to ensure balance across treatment arms, and at least 40% of subjects will be in each age group. Subjects will be assigned a randomization number by the

IVR/IWR system upon confirmation that the subject qualifies for enrollment in the Titration Period. Once a randomization number is assigned to a subject, the site will record the subject's initials and identification number on the corresponding study drug bottles. Each bottle will contain the assigned treatment (ZX008 or placebo). ZX008 and placebo will be identical, thus rendering the study drug and placebo indistinguishable. For each IMP bottle and randomization number assigned, the following information will be recorded on the drug accountability form: subject initials, unique bottle number, date each bottle is assigned, and drug used and unused during the study.

5.5.3 Cohort 2: Titration Period

The investigator (or delegate) will dispense IMP only to subjects included in this study following the procedures set out in this study protocol.

Study medication will be administered as equal doses BID in the morning and in the evening approximately 12 hours apart, with food. Each dose should be separated by a minimum of 8 hours and a maximum of 12 hours. A missed dose of study medication may be taken later up to 8 hours before the next scheduled dose; otherwise, the missed dose should not be given. Administration of the IMP will be based on the randomized dose and subject's weight at Visit 3 (Study Day -1). At Visit 8 (Day 50), if the subject's weight has changed $\pm 25\%$ of the weight at Day-1, the IMP dose will be recalculated. Subjects will be dosed using the oral dosing syringe provided.

The assigned 0.5 mg/kg/day (maximum 20 mg/day) dose for Cohort 2 was informed based on PK and safety data from Cohort 1, where single doses of 0.2 and 0.4 mg/kg together with data from Study ZX008-1505 were evaluated. In order to maximize tolerability, the dose for each subject will be titrated to 0.5 mg/kg/day. All subjects will start with a dose of ZX008 0.2 mg/kg/day (or placebo equivalent), administered in divided doses BID (maximum 20 mg/day) on Study Days 1-7. The dose will be increased to ZX008 0.4 mg/kg/day (or placebo equivalent) administered in divided doses BID (maximum 20 mg/day) on Study Days 8-14. The dose of ZX008 will be increased to 0.5 mg/kg/day (or placebo equivalent) administered in divided doses BID (maximum: 20 mg/day) on Study Days 15-21. The titration algorithm is shown in Table 5. See [Section 5.6](#) for more information about the volume of ZX008 or placebo to be administered.

Table 5. Titration Algorithm

Randomized Dose	Titration Step 1 Study Days 1-7	Titration Step 2 Study Days 8-14	Titration Step 3 Study Days 15-21
ZX008 0.5 mg/kg/day	ZX008 0.2 mg/kg/day	ZX008 0.4 mg/kg/day	ZX008 0.5 mg/kg/day
Placebo	Placebo	Placebo	Placebo

Note: maximum daily dose of ZX008 is 20 mg; the dosing regimen for all doses is BID

5.5.4 Cohort 2: Maintenance Period

After completion of the Titration Period, subjects will enter the Maintenance Period and continue to receive the randomized 0.5 mg/kg/day (maximum 20 mg/day) dose of ZX008 or placebo and be treated for an additional 12 weeks on stable dosage. Study medication will continue to be administered BID in the morning and in the evening, approximately 12 hours apart, with food. Each dose should be separated by a minimum of 8 hours and a maximum of 12 hours. A missed dose of study medication may be taken later up to 8 hours before the next scheduled dose; otherwise, the missed dose should not be given.

5.5.5 Cohort 2: Taper Period

Subjects who complete all of the Maintenance Period and will not be continuing into the open-label extension trial, and subjects who discontinue from the study early, will be tapered off of study medication over 8 days and will receive no study drug during the final 6 days of the taper period. Study drug administration will not be resumed after completion of the taper period. The taper algorithm is shown in [Table 6](#).

Table 6. Taper Algorithm

Randomized Dose	Taper Step 1 Days 1-4 after study completion or early termination	Taper Step 2 Days 5-8 after study completion or early termination	Taper Step 3 Days 9-14 after study completion or early termination
ZX008 0.5 mg/kg/day	ZX008 0.4 mg/kg/day	ZX008 0.2 mg/kg/day	No study drug administration
Placebo	Placebo	Placebo	No study drug administration

Note: maximum daily dose of ZX008 is 20 mg

Study medication will continue to be administered as equal doses BID in the morning and in the evening approximately 12 hours apart, with food. Each dose should be separated by a minimum of 8 hours and a maximum of 12 hours. A missed dose of study medication may be taken later up to 8 hours before the next scheduled dose; otherwise, the missed dose should not be given. IMP will be administered using the oral dosing syringe provided.

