QOLCE			X						X				X		
Healthcare utilization questions	X		X			X		X		X		X	X		
PEDsQL Generic Core Scale			X						X				X		
PedsQL Family Impact Module			X						X				X		
EQ-5D-5L (QoL of parent/caregiver)			X										X		
Randomize subject			X												
First Day of Study Drug Administration				X ^j											
Open-label consent form													X		
Daily Diary Completion								X							
Concomitant Medications									X						
Adverse events	X								X						
Adverse events of special interest	X								X					X ^k	

Table 2. Cohort 2: Schedule of Assessments (continued)

Study Assessments	Baseline Period ^a			Titration + Maintenance Period									EOS/ET ^b	Follow-up	Cardiac Follow-up ^c
	Screening	2 (Phone)	Randomization	Titration Period ^d			Maintenance Period								
Visit Number	1		3	4 (Phone or Clinic)	5	6	7 (Phone)	8	9 (Phone)	10	11 (Phone)	12	13	14	
Study Day	-43 to -42 or -42 to -41	-21	-1	1	8	15	22	36	50	64	78	92	106	TBD	3-6 mos post last study drug dose

AED=antiepileptic drug; BMI=body mass index; BRIEF=Behavior Rating Inventory of Executive Function; C=Collect; CBD=cannabidiol; CYP2D6=cytochrome P 450 2D6; D=Dispense; ECG=electrocardiogram; ECHO=echocardiogram; EOS=end of study; ET=early termination; EQ-5D-5L=standardized measure of health status; mos=months; PK=pharmacokinetics; QoL=quality of life; QOLCE=Quality of Life in Childhood Epilepsy; R=Review; THC=tetrahydrocannabinol

- a: The Baseline Period is comprised of the initial screening for the study and the assessment of baseline seizure activity recorded daily in the diary. The procedures to be completed at the Screening visit may be completed in a single day or split so that they are completed over the 2-day period (i.e., Days -43 to -42 or Days -42 to -41).
- b: Subjects who are discontinued early and those who complete the study and choose not to enroll in the separate open-label extension will be tapered off study medication over a 2-week period. Subjects who choose to continue in the separate open-label extension trial will undergo a 2-week transition period prior to enrollment.
- c: Follow-up ECG, ECHO, and physical examination will be performed 3-6 months after early termination, or for those subjects who complete the study but do not enter the open-label extension trial (see [Section 6.2.6](#)).

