- Collect plasma sample for background AED PK evaluation prior to the morning dose of study medication(s)
- Tanner Staging for subjects $>$ 7 years of age ([Appendix 5](#))
- Collect and review diary with parent/caregiver
- Dispense diary
- C-SSRS Children's Since Last Visit Assessment ([Appendix 2](#))
- CGI-I (assessed by parent/caregiver)
- CGI-I (assessed by investigator)
- Healthcare utilization questions
- Sleep quality and mealtime behavior questions
- Karolinska Sleepiness Scale ([Appendix 8](#))
- PedsQL Generic Core Scale ([Appendix 6](#))
- BRIEF ([Appendix 3](#))
- QOLCE ([Appendix 4](#))
- Parent/Caregiver QoL using the EQ-5D-5L scale ([Appendix 7](#))
- PedsQL Family Impact Module ([Appendix 6](#))
- Record AEs
- Record AESI

- Collect used, partially used and unused study medication; perform drug accountability and review with parent/caregiver
- Dispense study medication for taper for subjects not enrolling in the open-label extension trial
- Dispense study medication for transition for subjects enrolling in the open-label extension trial

Informed consent for the open-label extension trial must be signed at Visit 12 (if not signed earlier) in order to enter the open-label extension trial.

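### Table 6 sets the taper by randomized dose, so a ZX008 child who stops on titration Days 1-7 and is tapered would, as printed, go up from 0.2 to 0.4 mg/kg/day for 4 days

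*Protocol*

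**What the plan says.** Protocol Section 5.5.5 applies the taper to completers who do not enter the extension and adds that "subjects who discontinue from the study early, will be tapered off of study medication over 8 days". Table 6 has two rows, ZX008 0.5 mg/kg/day and placebo, under a column for the randomized dose. Its first dosing column is headed "Taper Step 1 Days 1-4 after study completion or early termination". The ZX008 row reads 0.4 mg/kg/day for 4 days, 0.2 mg/kg/day for the next 4, then no drug on Days 9-14, with a 20 mg/day maximum. SAP Section 3.2.2, Table 3, gives the same steps.

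Section 5.5.3 (Table 5) titrates ZX008 at 0.2 mg/kg/day on Days 1-7, 0.4 on Days 8-14 and 0.5 on Days 15-21, with the same cap.

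Tapering is the default after early discontinuation. Footnote b of the Cohort 2 schedule (Table 2) says: "Subjects who are discontinued early and those who complete the study and choose not to enroll in the separate open-label extension will be tapered". Section 4.5 asks the investigator to "attempt to complete all procedures usually required at the end of the study", and the list for that visit in Section 6.2.5.10 includes: "Dispense study medication for taper for subjects not enrolling in the open-label extension trial".

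Three passages qualify this:
- The synopsis (Duration of Treatment) describes the taper as a blinded reduction of dose in 4-day steps.
- Section 4.5 says that whether to stop at once or taper should be discussed with the Medical Monitor, and that "final decisions about the process will remain at the discretion of the site principal investigator".
- Section 5.1.1 says: "Dosing directions for the product can be found in the IMP handling instructions for the study subjects and for the investigator". Section 5.6 has the IVR/IWR system tell sites what volume to give.

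**The concern.** A taper should start at or below the dose being taken. Table 6 does so for a child who has reached 0.4 or 0.5 mg/kg/day, but it has no entry for a child still on 0.2. Followed literally, it raises the dose of a child who has just been withdrawn, possibly for an adverse event or worsening seizures, both of which Section 4.5 lists as reasons for discontinuation. The titration was built in for tolerability, and a step up on the way out works against that. At stake is the safety and exposure of a few children.

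**Working it through.** **The plan's own figure.** Table 6 gives 4 + 4 = 8 days on drug, and 8 + 6 = 14 days in all. This matches the 8 days in Section 5.5.5 and the 14-day taper period.

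**Inputs.** Titration doses come from Table 5; taper doses and the 20 mg/day cap come from Table 6. For weight w in kg, daily dose = min(mg/kg/day × w, 20 mg).

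**Stop on Days 1-7.** Compare min(0.2w, 20) before stopping with min(0.4w, 20) in Taper Step 1:
- 20 kg: 4 to 8 mg/day (2×)
- 50 kg: 10 to 20 mg/day (2×)
- 60 kg: 12 to 20 mg/day (20/12 = 1.67×)
- 80 kg: 16 to 20 mg/day (20/16 = 1.25×)
- 100 kg: 20 to 20 mg/day (no rise)

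The dose doubles up to 50 kg. Above that the cap shrinks the rise, and at 100 kg it is gone.

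**Stop on Days 8-14.** 0.4 to 0.4 mg/kg/day: level in Step 1, no rise.

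**Stop from Day 15 on.** 0.5 to 0.4 mg/kg/day: a step down. From 50 kg the cap holds both at 20 mg/day. No rise.

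**Total taper dose for a Day 1-7 stop.** Up to 50 kg, as printed: 4 × 0.4 + 4 × 0.2 = 2.4 mg/kg. Step 2 only: 4 × 0.2 = 0.8 mg/kg, a reduction of 1.6 mg/kg (1.6/2.4 = 67%). At 20 kg this is 48 mg against 16 mg. At 60 kg, with the cap, it is 4 × 20 + 4 × 12 = 128 mg against 4 × 12 = 48 mg.

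**Other text.** Section 4.5 offers an immediate stop or a taper and gives no other taper dose. Section 5.6 bases the volume on weight and does not say that it adjusts for the titration step reached. Neither document gives a taper dose other than those in Table 6 and SAP Table 3.

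**Number of children.** The documents give no week-1 discontinuation rate. For scale only, assuming 1% to 3% of about 45 ZX008 subjects gives 0.01 × 45 = 0.45 to 0.03 × 45 = 1.35 children, before removing those whose drug is stopped at once.

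**The case against.** The strongest reply is that the protocol plainly means a reduction. The synopsis has taper doses going down, and both Section 5.5.5 and the schedule footnote speak of tapering off. On this view Table 6 merely lacks a row, and the discretion in Section 4.5, which may extend to how to taper as well as whether to, lets a physician handle the rare case. No contact is scheduled between Day 1 and Day 8, so a taper begun in that window would need an unscheduled termination visit. The handling instructions and IVR/IWR rules may already deal with it.

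Much of this stands. A reader might infer that the protocol intends to double the dose in children being withdrawn, or that every week-1 leaver would receive the rise. The documents support neither: the synopsis points the other way, and the investigator may stop the drug at once. What remains is that an investigator who chooses to taper finds only one printed schedule, and for this child it goes up. If the unseen instructions correct it, the protocol should agree with them.

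It is also tempting to set the 2.4 mg/kg taper against drug already taken: 7 × 0.2 = 1.4 mg/kg by the end of Day 7 (1.7×), or 3 × 0.2 = 0.6 by the end of Day 3 (4×). These ratios overstate the matter, because the child was about to be titrated upward anyway. Up to 40 kg, where the cap does not bite, eight more days on study after Day 7 would give 7 × 0.4 + 0.5 = 3.3 mg/kg. After Day 3 they would give 4 × 0.2 + 4 × 0.4 = 2.4 mg/kg, and after Day 1, 6 × 0.2 + 2 × 0.4 = 2.0 mg/kg. The taper is therefore close to or below planned exposure. The fault is the direction of the step in a child leaving treatment.

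**Conclusion.** The point holds as a minor safety gap in the drafting. As printed, Table 6 and SAP Table 3 raise the dose from 0.2 to 0.4 mg/kg/day for 4 days in a ZX008 child who stops on Days 1-7 and is tapered. The dose doubles up to 50 kg, rises less between 50 and 100 kg, and does not rise from 100 kg. This conflicts with the synopsis.

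Confidence is high about what the table prints, and lower about what any one child would receive, since that depends on the investigator's choice and on instructions not in the documents. The number affected is unknown and probably very small; the illustration of roughly one child or fewer rests on an assumed dropout rate. The peak of 0.4 mg/kg/day is the dose due on Day 8 and is below the 0.5 target.

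A reader might also infer a threat to the efficacy result. There is none for the primary analysis: it uses the T + M period, and SAP Section 6.1.6 starts the taper the day after Visit 12, which is also the early termination visit.

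**What to change.** Add a footnote to Protocol Table 6, mirrored in SAP Table 3 for consistency:
- No taper dose may exceed the dose being taken at discontinuation.
- Subjects who discontinue on 0.2 mg/kg/day (Days 1-7) skip Step 1, take Step 2 (0.2 mg/kg/day for 4 days) and then stop, or stop at once. This is an exception to the 8-day wording in Section 5.5.5.

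Leave the taper unchanged for subjects on 0.4 or 0.5 mg/kg/day. They face no rise, and sending those on 0.4 to Step 2 would halve their dosed taper for no identified reason.

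Apply the same volume rule to placebo. The rule depends on the titration day, which blinded staff already know, so it reveals nothing about the arm. Match the IVR/IWR and the IMP handling instructions.

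The cost is a small protocol amendment plus the matching system rule and instruction line, with no added visits, subjects or procedures. Because it changes dosing for safety, it may count as substantial under Section 12.10 and need IEC/IRB approval before use. It can be bundled with another amendment.
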